| Research Question/ Aims: | 
Primary Aim:
 
 • To investigate patient experience of comfort during intraoral scanning versus alginate impression taking in the orthodontic setting. 
Secondary Aims:
 
 • To investigate patient experience of pain, relative speed of impression, nausea and/or coughing and whether the impression method could be recommended. • To investigate operator experience of ease, confidence, relative speed, and preference for intraoral scanning versus alginate impression taking in the orthodontic setting. • To investigate time taken to undertake an intraoral scan versus an alginate impression |

FUNDING AND SUPPORT IN KIND

| Funder(s) | Financial and Non-Financial Support Given |
|--|--|
| British Orthodontic Society Foundation | £11,081.08 |
| Derby Pump Priming Charitable Funds | £9,785.00 |

ROLES & RESPONSIBILITIES

Sponsor

The Sponsor, University Hospitals of Derby & Burton NHS Foundation Trust, take on overall responsibility for appropriate arrangements being in place to set up, run and report the research project. The sponsor is not providing funds for this study, but has taken on responsibility for ensuring finances are in place to support the research.

Funder

The study is funded by British Orthodontic Society Foundation (BOSF) and Derby Pump Priming Charitable Funds

Study Management Committees

Trial Management Group

The trial management group will meet regularly to oversee the day-to-day management of the trial, including all aspects of the conduct of the trial. Any problems with study conduct and participating centers will be raised and addressed during TMG meetings. The trial management group will include all research team members, clinicians involved in screening patients and a dental nurse representative. The study Trial Management Group will meet within the first month of trial commencement and every 2 months thereafter.

Protocol Contributors

A number of protocol contributors have been involved in the development of this protocol, these include; the Chief Investigator, Co-investigators, Statistician, Data Manager and Trial Manager.

Protocol contributors are responsible for inputting into the design of the study, ensuring that it is designed transparently and efficiently.

Contents

[figure not shown]
| | |
|---|----|
| SIGNATURE PAGE | 3 |
| KEY STUDY CONTACTS | 4 |
| STUDY SUMMARY | 6 |
| FUNDING AND SUPPORT IN KIND | 7 |

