As with any evolving technology within the dental profession, the lack of familiarity with the equipment can play a key role in the use of such equipment and deviation away from conventional methods. There are substantial costs involved, both long and short term and consideration then needs to also be given to the manufacturing of study models using the digital scans. Yet, digital scans can reduce the need for storage, disinfection and the 'mess' associated with conventional impression techniques (Christensen 2008). With regards to operator preference, Zitzmann et al. (2017) considered inexperienced dental students' perceptions towards both techniques. The students' preferences favoured digital impressions and they appeared to learn the skill of digital impression taking quicker than conventional impressions. Schott et al. (2019) also explored the student perspective on both techniques and demonstrated the lack of significant difference between the methods from both the clinician and patient perspective, although there was a preference by the students for the digital technique (58.1%). Although based on prosthetic treatment, a study suggested that digital impression techniques were "less time consuming and more convenient" for the clinician and showed statistically significant advantages in terms of recording occlusal contacts, which can be applicable for orthodontic cases (Gjelvold et al. 2016). In terms of which intraoral scanner is preferred, Park et al. (2015) investigated this. The results showed the participants preferred the Trios scanner over the iTero scanner on a number of parameters. Additionally, it demonstrated that training in the use of the scanner changed the views of the participants (dental hygienists) in a positive way.

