2. RATIONALE

Intraoral scanners are becoming more popular within orthodontic settings, both primary care and secondary care. There are benefits of digital scanning systems such as a reduced environmental impact and reduced storage need but there is limited evidence regarding patient centred outcomes such as comfort in the UK population. Patient-centred care is vital and having a sound evidence-base

is imperative in a clinician's decision towards investing in the equipment and training required. In addition, patient outcomes can feed into future development of the scanners to ensure that patient comfort remains at the forefront. The research will also consider operator preferences which is also highly critical in terms of acceptance of new equipment and its use within a team. The proposed study will aim to add to the limited evidence base, providing information to the orthodontic community regarding the use of intraoral scanners compared to alginate impressions from both the patient and operator perspectives.

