10.3.2. Outcome Analysis

The primary outcome

The primary endpoint is the difference between two (identical) visual analogue scales (VAS) measuring the comfort of each procedure. One VAS will measure the comfort of the impression and the other VAS will measure the comfort of the scan. Each VAS will be measured by two operators and a mean of their measurements will be recorded for each scale. The difference between each participant's mean comfort VAS scores will be calculated. The mean of the differences will be reported for each treatment sequence with 95% confidence intervals.

The difference between the paired VAS will be compared using analysis of variance (ANOVA) that will analyse the period, treatment and sequence effects of the comfort scores. Analysis of the primary endpoint will be assessed using 2-sided 0.05 levels, consistent with the type I alpha level used in the trial design.

The secondary outcomes

- Four modified 100mm VA scales to measure the participant's experiences of:
 - Pain;
 - Relative speed of impression;
 - Nausea and/or coughing;
 - Whether the impression method could be recommended; and
- Four 100mm VA scales to measure the orthodontic operator's experience of:
 - Ease of impression;
 - Confidence taking the impression;
 - Relative speed of impression; and
 - Whether the participant felt sick or coughed during the procedure.
- The time taken to make the impression or complete the scan will be recorded (mins)
- A simple question to determine operator preference for intraoral scanning versus alginate impressions.

The 8 secondary outcomes measured by VAS and the time taken to make the impression or complete the scan will be compared using analyses of variance suitable for a crossover study, that will test the period, treatment and sequence effects on these nine secondary outcomes. The mean differences between the paired VAS scores (e.g., Pain from scan and pain from impression) will be reported with 95% confidence intervals.

The operator's preference will be reported using descriptive statistics. The frequency and percentages will be recorded.

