[E.2] Definition of Primary Endpoint [Protocol Sec. 10.3.2]

[E.2.1] The primary endpoint is the difference between two (identical) visual analogue scales (VAS), both completed by the patient, measuring the comfort of each procedure. One VAS will measure the comfort of the impression and the other VAS will measure the comfort of the scan. Each VAS will be measured by two operators and a mean of their measurements will be recorded for each scale. The difference between each participant's mean comfort VAS scores for the two procedures will be calculated.

[E.3] Statistical Methods for Primary Analysis [Protocol Sec. 10.3.2]

[E.3.1] The mean of the differences between procedures will be reported for each treatment sequence with 95% confidence intervals. The difference between the paired VAS will be compared using analysis of variance (ANOVA) that will analyse the period, treatment and sequence effects of the comfort scores. Analysis of the primary endpoint will be assessed using 2-sided tests with a significance level of 0.05.

[E.4] Definition of Secondary Endpoints [Protocol Sec. 10.3.2]

[E.4.1] Patients will complete 4 secondary endpoints, each of which will be measured using two (identical) VAS, both completed by the patient, to measure four different features of each procedure (see section E.4.2 for details of the features the patients will assess). For each assessment, a VAS will be scored for the impression and another for the scan. Each VAS will be measured by two operators and a mean of their measurements will be recorded for each VAS.

[E.4.2] The patients will assess

1. pain
2. the speed of the procedure,
3. nausea and / or coughing
4. to what degree the patient would recommend the procedure

[E.4.3] Orthodontic operators will complete 4 secondary endpoints, each of which will be measured using two (identical) VAS, both completed by the operator, to measure four different features of each procedure (see section E.4.4 for details of the features the operators will assess). For each assessment, one VAS will be a measurement of the impression and the other will measure the scan. Each completed VAS will be measured by two operators (using rulers) and a mean of their measurements will be recorded for each scale.

[E.4.4] The operators will assess

1. Ease of impression
2. Confidence taking the impression
3. Relative speed of the impression
4. whether the patient felt sick or coughed during the procedure

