[E.4.5] The time taken to make the impression or complete the scan will be recorded (mins)

[E.4.6] A secondary analysis of the primary outcome will be undertaken using a two-period two-treatment mixed effects model.

[E.4.7] If some participants have not complied with the protocol, a second analysis of the primary outcome will be conducted just including participants that were compliant.

[E.5] Statistical Methods for Secondary Analyses [Protocol Sec. 10.3.2]

[E.5.1] Eight of the secondary outcomes will be recoded using VAS scores (see Sections E.4.2 and E.4.4). The differences between the paired VAS scores of these secondary outcomes will be reported using means and 95% confidence intervals. They will be compared using analysis of variance (ANOVA) that will analyse the period, treatment and sequence effects of the comfort scores. Analysis of the secondary endpoint will be assessed using 2-sided tests with a significance level of 0.05.

[E.5.2] The mean difference in the time required for each procedure (Section E.4.5) will be reported, with 95% confidence intervals. The difference in time will be compared using analysis of variance (ANOVA) that will analyse the period, treatment and sequence effects of the comfort scores. Analysis of the secondary endpoint will be assessed using 2-sided tests with a significance level of 0.05.

[E.5.3] The operator's preference for each impression (Section E.4.6) will be tabulated and reported using frequencies and percentages.

[E.5.4] The secondary analysis of the primary outcome using a two-period two-treatment mixed effects model (Section E.4.7) will be undertaken with participant effects treated as random and a treatment-by-period interaction (for this analysis, the carryover effect) included in the model. The mean effects will be reported, with 95% confidence intervals.

[E.5.5] The potential second analysis of the primary outcome (Section E.4.8) will be a per protocol analysis of the difference between the paired VAS. This will be carried out using an analysis of variance (ANOVA) that will analyse the period, treatment and sequence effects of the comfort scores. Analysis of the primary endpoint will be assessed using 2-sided tests with a significance level of 0.05. The mean effects of this model will be reported, with 95% confidence interval

[E.6] Statistical Methods for Sub-group Analyses [Protocol Sec. 10.4]

[E.6.1] There will be no sub-group analyses

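### Do the operator-rated scales and procedure time need an operator term in their analysis?

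*Protocol*

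**What the plan says.** Protocol 10.3.2 has nine secondary outcomes on a continuous scale: four VAS completed by the patient, four completed by the operator, and procedure time. They are to be compared "using analyses of variance suitable for a crossover study, that will test the period, treatment and sequence effects on these nine secondary outcomes".

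SAP E.5.1 says of the eight scales: "The differences between the paired VAS scores of these secondary outcomes will be reported using means and 95% confidence intervals". SAP E.5.2 says of time: "The mean difference in the time required for each procedure (Section E.4.5) will be reported, with 95% confidence intervals". Both sections add: "Analysis of the secondary endpoint will be assessed using 2-sided tests with a significance level of 0.05". SAP E.4.3 settles who does the rating: "Orthodontic operators will complete 4 secondary endpoints".

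No operator effect, clustered error or operator-level summary is planned. The only random effect named is participant, in a secondary model of the comfort score, and Protocol 10.5 rules out adjusted analyses.

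Two statements bear on how much this matters. Protocol 10.3.2 reserves formal significance for the primary analysis and treats the secondary analyses as hypothesis generating. Protocol 7.6 says the clinicians and nurses will be trained in the protocol and calibrated.

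The documents do not state how many operators there are, how cases are shared, or whether one operator does both visits for a participant. The case report form contents in Protocol 9.1 are headings rather than fields. The questionnaires are not in the documents, so operator identity may already be recorded.

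**The concern.** One operator supplies many of the paired ratings. If operators differ in their scan-minus-alginate difference, ratings by the same operator are correlated, and an analysis that counts every participant as independent overstates the information about operators in general.

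The protocol gives some reason to ask. Operator experience is a stated secondary aim (Study Summary: "To investigate operator experience of ease, confidence, relative speed"). The rationale speaks of "providing information to the orthodontic community regarding the use of intraoral scanners compared to alginate impressions from both the patient and operator perspectives". The background reports of one scanner study that "it demonstrated that training in the use of the scanner changed the views of the participants". Protocol 7.6 only requests that staff complete at least 10 scans beforehand.

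At stake are the width of the confidence intervals and the true level of the 0.05 tests for the four operator scales and for time. The four patient-rated secondary scales are not part of this point.

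**Working it through.** **1. The plan's own figure.** Protocol 10.1 gives an SD of 29.85 mm, a difference of 11 mm, alpha 0.05 and power 0.9. Reading the SD as that of the within-participant difference:

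n = ((1.960 + 1.282) × 29.85 / 11)² = 77.4, so 78 in total and 39 per sequence, as stated.

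With 7% dropout this gives 42 per sequence and 84 in total. The calculation concerns the comfort score only, so nothing below affects it.

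**2. Which operator variation matters.** Write the paired difference for a participant seen by operator j as μ + g_j + e.

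- A tendency common to both methods (generous, confident, fast) cancels if one operator does both visits. Otherwise it adds to the spread that the planned standard error already measures. Simulated type I error with such effects alone was 4.7% to 5.2%.
- Only g_j, the operator's own scan-versus-alginate difference, can do harm.

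**3. Reading A: operators in general.** Assume k operators with equal caseloads, and let ICC be the share of the variance of the paired difference due to g_j.

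Design effect = 1 + (78/k − 1) × ICC

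At ICC 0.05:

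- k = 2: 1 + 38 × 0.05 = 2.90
- k = 4: 1 + 18.5 × 0.05 = 1.93
- k = 8: 1 + 8.75 × 0.05 = 1.44

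The planned standard error is also estimated slightly low, because the sample variance is reduced by the factor 1 − (78/k − 1) × ICC / 77. For k = 4 the ratio of true to planned standard error is √(1.925 / 0.988) = 1.40. It is 1.72 for k = 2 and 1.20 for k = 8.

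Simulated type I error of the nominal 5% test (20,000 replicates per setting, 39 + 39 participants, 76 degrees of freedom):

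| Operators | ICC 0 | ICC 0.01 | ICC 0.05 | ICC 0.2 |
|---|---|---|---|---|
| 2 | 4.6% | 9.9% | 24.8% | 52.2% |
| 4 | 5.2% | 7.2% | 15.5% | 37.4% |
| 8 | 4.9% | 6.0% | 10.1% | 23.7% |

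Every k and every ICC here is an assumption.

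For scale, borrow the comfort SD. The planned half-width is about 1.99 × 29.85 / √78 = 6.7 mm. It would need to be about 6.7 × 1.40 = 9.4 mm at k = 4 and ICC 0.05, before allowing for few degrees of freedom.

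**4. Reading B: the participating operators.** Hold the g_j fixed and take the target as their caseload-weighted mean. The spread between operators then sits in the residual and makes the test slightly conservative. Type I error was 3.0% to 5.1%. Coverage of the 95% interval was about 95% to 97% with the same operator at both visits.

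**5. Different operators at the two visits.** With ICC 0.05 and an assumed common operator effect of SD 15 mm, coverage on reading A was 80%, 89% and 95% for 2, 4 and 8 operators. With the same operator throughout it was about 76%, 84% and 90%. Part of the shortfall can therefore disappear under a visit pattern that the documents leave open.

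**6. What a valid analysis for reading A costs.** A t-test on operator means (k − 1 degrees of freedom) holds 4.7% to 5.2% in all settings. Its interval at ICC 0.05, relative to the planned one, is 8.8 times as wide with 2 operators, 2.9 with 3, 2.1 with 4 and 1.4 with 8.

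**The case for a change.** The case for a change is that the sponsor should either model operator-by-procedure variation or say that the result applies to these operators only, and the plan does neither. Calling an analysis hypothesis generating does not widen an interval that is too narrow, and the SAP attaches a 0.05 level to these outcomes despite the protocol's wording. Operator identity not noted at the visit may be hard to recover later.

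The factual parts stand: no operator term exists, the restriction is not written down, and the conditional arithmetic is right. The inference from them is weaker.

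- The rationale names an audience, not a target of inference to a sampled population of operators. The trial also uses one hospital, one scanner model and one alginate, and no one would ask for random terms for those. How far one department's results carry is a limitation to discuss in the report.
- The background evidence is indirect. The training study concerned dental hygienists' views of scanners and reported a positive shift after training. It did not report that operators differ in how scanning compares with alginate. The remark on familiarity is about uptake of equipment. Training and calibration under Protocol 7.6 act against such differences.
- The remedy does little where the inflation is largest. With 2 or 3 operators the extra terms cannot usefully be estimated, and all that remains is a sentence on scope.
- The mismatch between the SAP's 0.05 level and the protocol's description of the secondary analyses is a separate matter, which an operator term would not resolve.

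**Conclusion.** No change to the plan follows. The planned intervals are valid for the operators who take part (type I error 3% to 5%). They are too narrow only if operators differ in their scan-versus-alginate difference and the result is also generalised to other operators. On that wider reading the true level could lie anywhere from 5% to about 52% across the assumed range of 2 to 8 operators and ICC 0 to 0.2. The documents give nothing to narrow that range.

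Treating operators as fixed or random is a choice on which experienced statisticians differ. Here random operators would cost intervals 1.4 to 8.8 times as wide (8 down to 2 operators, ICC 0.05) for five secondary, hypothesis-generating outcomes. Stating the number of operators and their caseloads, and wording the conclusion for those operators, is ordinary reporting that an analyst can do without an amendment. The primary comfort analysis and the sample size of 84 are not touched.

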10.4. Subgroup Analyses

There will be no subgroup analyses.

10.5. Adjusted analyses

There will be no adjusted analyses.

10.6. Interim Analysis and Criteria for the Premature Termination of the Study

There will be no interim analyses.

The Sponsor may suspend or prematurely terminate either the entire study, or the study at an individual site, for significant reasons that must be documented (e.g. an unacceptable risk to participants or serious repeated deviations from the protocol/ regulations). If this occurs the Sponsor shall justify its decision in writing and will promptly inform any relevant parties (i.e. participants, investigators, participating sites, REC, regulatory bodies).

10.7. Analysis Groups

All participants who were randomised and experienced at least one of the study treatments will be included in the primary analysis. Participants will be analysed according the treatment sequence they received, if this differs from the treatment sequence to which they were allocated.

The potential re-analysis of the primary analysis will be carried out on a per protocol basis (i.e. only participants without major protocol deviations who completed the study with the treatment that was originally allocated will be included).

All participants who completed the study will be included in the other secondary analyses. Participants will be analysed according the treatment sequence they received, if this differs from the treatment sequence to which they were allocated.

10.8. Procedure(s) to Account for Missing or Spurious Data

Once identified as eligible, participants will receive two appointments a minimum 4 weeks apart from one another. Having the appointment time and date early, allows for the participant and their parent or guardian, if appropriate, to plan around school and work as much as possible. Prior to their appointments, they receive a text message reminder from the hospital. Any missed appointments will be managed in line with local policy, particularly concerning safeguarding of children and vulnerable adults.

If there are missing data in the primary endpoint, then multiple imputation using chained equations will be applied. The plausibility that outcome data are missing at random (MAR) from the primary endpoint will be examined, and if it doesn't hold, sensitivity analysis will be conducted. A complete case analysis will be performed for secondary trial outcomes.

11. MONITORING, AUDIT & INSPECTION

As a low-risk study, a monitoring plan is not required.

12. ETHICAL AND REGULATORY CONSIDERATIONS

12.1. Assessment and Management of Risk

The benefit of participating on the trial is the ability of the participant to help provide their first-hand experience of a very commonly carried out orthodontic procedure. Better understanding from a patient's perspective can be useful to the clinician as well as to manufacturers of impression materials and intraoral scanning devices in future development. A patient undergoing orthodontic treatment within the department would require an intraoral scan and often an addition alginate impression as part of their normal care, and therefore participation would not significantly deviate away from this.

The exclusion criteria have been selected to prevent bias within the study and to exclude those patients that a scan or impression may be carried out differently within their normal orthodontic care. Those that have previously had scans or impressions in the last 2 years may already have an experience which could influence their questionnaire answers. Those with cleft lip or palate, may require modifications of the normal impression methods and therefore inclusion within the study would put them through extra treatment, which for them may not be as comfortable.

Due to the need to complete questionnaires and gain informed consent and assent, appointments with the participant may be slightly longer. We have, therefore, have tailored the washout period between appointments to a time period that would fit with a patient's normal orthodontic appointments, so as to limit the number of times the patient would have to come into the hospital and reducing the time missed at work or school. The average overall time for orthodontic treatment for a patient is 2-2.5 years and the study itself does not anticipate extending this beyond what would normally be required by the patient.

The visual analogue scale used to collect information from the participants following the intraoral scan or impression will be modified with pictorial anchors to help patient understanding, particularly if the participant is a child. This will be piloted to check health literacy, ease of use and clarity of instructions and amended accordingly.

Low risk is anticipated by participating in the trial.

- There is a risk of participant's coughing or gagging during both procedures, with the potential for aerosol generation.
 - The team treating the participants will follow necessary protocols, including that of personal protective equipment, in line with COVID processes.
 - Any accompanying individuals/parents of the participant will be asked to wait outside the department, limiting footfall within the surgery.
 - If the participant does gag during an impression or intraoral scan, the clinician will implement measures to reduce this as much as possible and to ease any anxiety by the participant.
 - There are only isolated cases of allergic reaction to alginate materials. The incidence of such reactions is unknown due to the lack of published evidence (Syed 2015)
 - To reduce the risk of this occurring, the clinician will check known allergies and medical history with the participant and/or the parent/guardian as part of their normal orthodontic treatment and this information can then be highlighted.

